1. PROVIDER MEASURES

provider data collection will span the training sequence, and active implementation and sustainment phases (18 months in total- see Timeline). Data will include provider quantitative surveys and qualitative data interviews, fidelity assessments of recorded TF-CBT

sessions (via objective coding), and ratings of TF-CBT cases presentation completed by TF-CBT consultants. Data collection will be incentivized in both the implementation and sustainment phase.

Quantitative surveys. Provider surveys will be administered via a secure web-based system, RedCap, at 12 time points. Providers will self-report (list of measures below) their demographic characteristics, BASIS mechanisms (attitudes, subjective norms, self-efficacy, maintenance self-efficacy), implementation intentions, organizational moderators (implementation climate, leadership) and TF-CBT sessions delivered.

Research Questions for Data Collection During Clinicians Training

Surveys will be self-administered by providers through RedCap during:

T1-T5 (Training sequence data collection) Measures

BASIS Mechanism:

1. Attitudes: [EBPAS \(Evidence-Based Attitudes Scales\)](#)
2. Intentions: [Modified Intention to Use Scale](#)
3. Self- efficacy: [Modified Teacher Self-efficacy Scale \(Practitioner Self-efficacy Scale\)](#)

4. Subject norms: Modified Subjective Norms Measure (descriptive and injunctive)

T5 only: MEAT/IOTTA

T6 (3-4 weeks after training, school context data collection) Measures

BASIS Mechanism:

1. Attitudes: [EBPAS \(Evidence-Based Attitudes Scales\)](#)
2. Intentions: [Modified Intention to Use Scale](#)
3. Self- efficacy: [Modified Teacher Self-efficacy Scale \(Practitioner Self-efficacy Scale\)](#)
4. Subject norms: Modified Subjective Norms Measure

Outcome Measure:

1. [S-ICS \(School Implementation Climate Scale\)](#)
2. [S-ILS \(School Implementation Leadership Scale\)](#)
3. Adoption and penetration
4. Intervention and Usability Scale
5. Time Allocation Questionnaire

T7-T9 (implementation phase: 3, 6, 9 months data collection) Measures

BASIS Mechanism:

1. Attitudes: [EBPAS \(Evidence-Based Attitudes Scales\)](#)
2. Intentions: [Modified Intention to Use Scale](#)
3. Self- efficacy: [Modified Teacher Self-efficacy Scale \(Practitioner Self-efficacy Scale\)](#)
4. Subject norms: Modified Subjective Norms Measure

Outcome measures:

1. Compatibility and Identity Questionnaire

2. Time Allocation Questionnaire
3. Adoption and Penetration Survey

Outcome measures T8 and T9

4. Intervention usability scale

T10-T12 (sustainment phase: 12, 15, 18 months data collection) Measures

BASIS Mechanism:

1. Attitudes: [EBPAS \(Evidence-Based Attitudes Scales\)](#)
2. Intentions: [Modified Intention to Use Scale](#)
3. Self- efficacy: [Modified Teacher Self-efficacy Scale \(Practitioner Self-efficacy Scale\)](#)
4. Subject norms: Modified Subjective Norms Measure

Outcome Measures:

1. Compatibility and Identity Questionnaire
2. Time allocation questionnaire
3. Adoption and penetration survey

Outcome Measure (only collected during T10):

1. [S-ICS \(School Implementation Climate Scale\)](#)
2. [S-ILS \(School Implementation Leadership Scale\)](#)
3. Intervention usability scale

Tracking across these time points is critical to determining whether and when the effects of BASIS on its target mechanisms may fade, as well as the longitudinal relationship among these mechanisms, moderators, implementation outcomes, and clinical outcomes.

Timepoint	BASIS Mechanism:	MEAT/ IOTTA	Outcome Measures:	Outcome Measures:	Outcome Measures:	Outcome Measures: Time	Outcome Measures: Compatibility
	1. Attitudes						

	2. Intentions 3. Self-efficacy 4. Subjective norms		1. S-ICS 2. S-ILS	Adoption and Penetration	Intervention and Usability Scale	Allocation Questionnaire	and Identity Questionnaire
T1	X						
T2	X						
T3	X						
T4	X						
T5	X	X					
T6	X		X	X	X	X	
T7	X			X		X	X
T8	X			X	X	X	X
T9	X			X		X	X
T10	X		X	X	X	X	X
T11	X			X		X	X
T12	X			X		X	X

2. STUDENT & CAREGIVER MEASURES

Student & Caregiver data collection will focus on mental health and functional outcomes targeted by TF-CBT. The RAs, PCs, or RC will contact families via phone to complete a REDCap survey. Student & caregiver measures will examine three different TF-CBT mechanisms and outcomes, collected at all data collection time points (T6, T7, T8); with demographics being collected at T6. At the end of the school year, academic records will be requested for all students who received TF-CBT during that year. Students' attendance, discipline, and achievement (standardized test scores, grades) will be extracted from these academic records.

Timeline for Collection

T6: Baseline (After to 1 st appt with clinician, and before 2 nd appt with clinician) (\$20)		T7: 3 month (\$20)		T8: 6 month (\$20)	
Student	Caregiver	Student	Caregiver	Student	Caregiver
Consent/Accent					
Demographics					
Strengths & Difficulties Questionnaire (SDQ)		SDQ		SDQ	SDQ
Moods and Feelings Questionnaire (MFQ)		MFQ		MFQ	MFQ
Child PTSD Symptoms Scale for DSM-V (CPSS-5)		CPSS-5		CPSS-5	CPSS-5
Emotional Regulation Questionnaire (ERQ-CA)	Parent Emotional Reaction Questionnaire (PERQ)	ERQ-CA	PERQ	ERQ-CA	PERQ
Child Post-Traumatic Cognitions Inventory (CPTCI)		CPTCI		CPTCI	
Post Traumatic Avoidance Behavior Questionnaire (PABQ)		PABQ		PABQ	

TF-CBT Mechanism:

1. Belief change: [Long Version CPTCI \(Child Posttraumatic Cognitions Inventory\)](#)
2. Behavior avoidance: PABQ (Posttraumatic Avoidance Behavior Questionnaire) (Van Minnen & Hagenaars, 2010)
3. Emotion regulation: ERQ-CA (Emotional Regulation Questionnaire- Child & Adolescents)

Outcome measure:

1. [CAPS \(Children's Attributions and Perceptions Scales\)](#)
2. [CPSS-V Self Report \(Child PTSD Symptom Scale DSM-V\)](#)

3. [CSCY \(Coping Scale for Children and Youth\)](#)
4. [Long Version MFQ Self Report \(Moods and Feelings Questionnaire\)](#)
5. [SDQ Self Report \(Strengths and Difficulties Questionnaire\)](#)

SECTION FIVE: QUALITATIVE DATA COLLECTION AND ANALYSIS: RECORDING AND CODING

2. PROVIDER INTERVIEW

Individual semi-structured zoom interviews (approximately 30-45 minutes) were conducted at a convenient time for identified providers. The interview was recorded via zoom. Recordings were transcribed prior to coding by the staff with the use of zoom audio transcriptions. The mixed methods design was sequential in structure (quantitative data collected prior to qualitative data); the functions are sampling (using quantitative data to identify our qualitative sample- participants randomly choose based on if they started or didn't start TF-CBT) and expansion (using qualitative data to provide depth and breadth of understanding of the factor that contribute to provider outcomes that deviate from our theory of change; and the process is connecting (the qualitative dataset will build on the quantitative dataset). Qualitative data will explore the limits of- and potentially refine the BASIS theory of change. We developed a systematic, comprehensive semi-structured interview guide that draws from EPIS framework to examine multilevel (i.e., interventions, individual, inner setting, outer setting) determinants that explain what processes facilitated or hindered EBT implementation and sustainment. We generated questions that explore the most salient implementation or sustainment determinants and mechanisms, and how TPB variables may interact with other relevant characteristics of the implementation setting. Questions will be carefully constructed to elicit clear information without assigning valence to implementation/sustainment.

	Aim 1b: Evaluate main effects on child mental health outcomes (symptoms of PTSD, depression, anxiety) and test intervention mechanisms via a mediational model.	Multilevel Model 
Independent: RETI vs TF-CBTDependent: Child measured outcomes (CPSS-V (child and CG, SMFQ (child and CG))

		
 • Nesting: student under provider, time • Mediator: BASIS Mechanism (provider-level data) 
** There will be four different models- 1) base model with only intercept, 2) model with only IV, DV, and time, 3) model with IV, DV, time, and TF-CBT vs RETI interaction with time, and 4) lastly, IV, DV, and study group interaction (BASIS, AC, RETI) with time.

	Aim 1c: Evaluate the cost and cost-effectiveness of TF-CBT for improving clinical outcomes	

Main aim	Sub aim	Analysis method
Aim 2: Experimentally evaluate the impact of BASIS versus Attention Control (AC).	Aim 2a: Evaluate main effects on proximal implementation mechanisms of change (attitudes, subjective norms, self-efficacy, intentions to implement, and maintenance self-efficacy).	
Multilevel model
 
 • Independent (IV): AC vs BASIS • Dependent (DV): attitudes, subjective norms, self-efficacy, intentions • Nesting: Piecewise time (training, active, sustainment) • Interaction: Time X Study group 
 ◦ T1 to T5 X BASIS ◦ T6 to T9 X BASIS ◦ T10 to T12 X BASIS 
** There will be four different models- 1) model with only intercept, 2) model with only IV, DV, and time, 3) model with IV, DV, and study group interaction (BASIS, AC) with time, 4) 3) lastly, model with IV, DV, and study group interaction (BASIS, AC, and RETI) with time.


Aim 2b: Evaluate main effects on objective implementation outcomes (adoption, fidelity, sustainment) and test implementation mechanisms via a mediational model.
	
Cross tabulation
 
 • Difference in TF-CBT adoption among BASIS and AC groups. • Include missing as 0 • Sensitivity analysis will exclude missing 
Survival analysis
 
 • The difference in adoption for TF-CBT is adopted among BASIS and AC groups. 
Fidelity
 
 • Difference in TPOCS scores among BASIS and AC groups (there was no significant finding due to lack of data) • One row per provider (did the provider in any tape use TF-CBT content, because there isn't enough provider data to run a multilevel mixed method analysis)

Aim 2c: Conduct sequential mixed-methods data collection to explain residuals (i.e., clinicians whose implementation behavior is unaccounted for by the mediation model).
	
Qualitative analysis
 
 • Consensus coding of qualitative interviews • Pulling out main themes

Aim 2d: Evaluate the cost and cost-effectiveness of BASIS for improving clinical outcomes.

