1. CONDITIONS OVERVIEW

Providers were randomized to one of two TF-CBT conditions or a RETI (Resource Efficient Trauma Intervention) condition. Those randomized to TF-CBT will receive either BASIS + TF-CBT or Attention control (AC) + TF-CBT. Both BASIS and AC bookend the TF-CBT 3-day training and will be followed by an online booster session. TF-CBT gold-standard training and 6 months of follow-up consultation were delivered by [name], [name], and [name].

Three Research Groups

BASIS plus TF-CBT (B + TF-CBT)

Providers in this research condition received the BASIS intervention prior to and post TF-CBT training.

Attention Control plus TF-CBT (AC + TF-CBT)

Providers in this research condition received attention control prior to and post TF-CBT training.

Resource-Efficient Trauma Intervention (RETI)

Providers in this research group received a half-day training and handout in RETI practices.

Clinical Interventions

RETI

Resource-Efficient Trauma Intervention (RETI) can be described as scaffold treatment-as-usual. It is a less prescriptive and resource-intensive intervention. It includes four core components – initial assessment, psychoeducation, social connection, and planning – which involve identifying which students have trauma exposure, connecting them to a practitioner who provides psychoeducation and social support, and the development of a support plan. This second approach provides school service providers with greater flexibility and autonomy but has been tested less extensively.

TF-CBT

TF-CBT was selected based on its established evidence and the stated need of participating districts to address student trauma and increasing concerns about student safety. TF-CBT is a 12-16 session intervention for students aged 3 to 18 years with trauma-exposure and related mental health sequelae. TF-CBT includes individual sessions for the youth, individual sessions for parents, and conjoint sessions that include involvement. The first third of TF-CBT focuses on psychoeducation and developing coping skills to reduce trauma-

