1. AC + TF-CBT

Providers randomly assigned to AC + TF-CBT will receive a 3-hour pre-training, 45-min post-training session, and an online booster 30-days post training to mirror the duration of BASIS and provide control providers with comparable amounts of attention. The in-person or virtual components of AC will be delivered by the same facilitator as BASIS ([name]) to control for facilitator effects. Content will be didactic, as in typical training for school mental health providers. The AC pre-training will provide content on the definition of Evidence-Based Treatment (EBT), how EBTs are established, why providers should use EBTs, clinical outcomes associated with different EBTs, and defining different dimensions of fidelity. The post-training session will involve having control providers reflect on TF-CBT, its core components, and discuss the outcomes associated with TF-CBT. The AC booster will prompt providers to reflect on and describe TF-CBT and identify and define each of its core components. The AC condition thus controls for dose, information provided, and interventionist effect.

1.2 Pre-Training Activities for internal teams:

2-4 Months Before Training (Ordinal Tasks must be completed in order; assumes dates have been set)

- Collect school demographics information

- Send Provider Baseline, give 1-2 weeks for completion
- Complete and ship goodie bags to district administrators
- Randomize Providers based on baseline and demographics information

1 Months Before Training

- Send Self-Paced Training link for those who are in TF-CBT
- Send out Zoom link and training calendar invites to /trainers
- Send reminder email for SPT link and reiterating dates for trainings

2 Weeks Before Training

- Check SPT completion rates, send reminders as needed
- Check-in with trainers
- Send out Zoom link and training calendar invites to participants/trainers

1 Week Before Training

- Reminder sent, links for training included
- T1 sent for completion
- Send YouTube training videos for research activities
- Friday before training – check for SPT completion and send reminders as needed

Training Day

- Send out Self-Paced Training gift cards for TF-CBT participants
- Check all T1 completion, send reminders to those who did not complete
- During training first 5 minutes: call on those who have not completed T1 to take time to complete T1
- Following training: send out T2 surveys to be completed by following morning for TF-CBT

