- Following training: send out T5 surveys, payment, and relevant information for RETI participants

RANDOMIZATION

Providers and student random assignments occurred at the school level, with one provider per school recruited for the first year, and multiple people per school building was recruited for year two and three. We use this strategy to minimize analytic difficulties associated with reliably partitioning school and provider variance with small numbers of providers per school. Providers and TF-CBT trainers/consultants would be blinded to their BASIS condition assignment. To ensure comparability of conditions at baseline, minimize potential confounding, and maximize accuracy of effect estimates, we used a blocked randomization design. Schools were first blocked by state (WA, MN, IN, KY, WI, VT, PA, AZ, and MD) and district. We collected baseline provider data on implementation intentions and TPB and HAPA mechanisms (e.g., attitudes, norms, self-efficacy), identify matched pairs using these variables, and randomly assign providers within pairs to condition. Students were placed into TF-CBT or RETI based on the condition into which their school's existing SMH provider was randomized.

SECTION THREE: RECRUITMENT AND CONSENTING

SCHOOL DISTRICT

Participating schools (n=133) are located across multiple states. Schools are situated in diverse settings, including rural (n=1), suburban (n=2), and urban (n=2) regions and have total enrollments of 9,658 - 37,971 students. Student populations are diverse overall, with a mean of 44% of students identifying as racial/ethnic minorities (range 30% to 60%)

PROVIDER

Provider participants include 191 school mental health providers who were consented and randomized, but only 146 completed the BASIS+TF-CBT, AC+TF-CBT, RETI training to continue in the study. Provider recruitment across all three waves will occur with the assistance of district administrators. Principals will provide us with the email addresses of school mental health providers for recruitment.

1. Provider SCREENING CRITERIA

In order of preference:

1. Dedicated mental health providers that have regular individual psychotherapy sessions

- a. The school employed favorable over CBO (Community Based Organization), but CBO is a close second
2. People who devote some, but not all of their time to direct service delivery with students (e.g., pulling kids out and doing interventions), like...
 - a. School Social Worker;

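### Aim 2a, Model 4: RETI providers appear to have only T1 and T5 in the training phase, so a training-slope comparison with BASIS and AC can make equal gains look different (minor, secondary model)

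*Combined protocol and SAP*

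**What the plan says.** Section Six sets the Aim 2a contrast as "Independent (IV): AC vs BASIS" and the time structure as "Nesting: Piecewise time (training, active, sustainment"). The first listed interaction term is "T1 to T5 X BASIS", so the training piece runs from T1 to T5. Model 3 covers BASIS and AC. Model 4 adds the third arm: "study group interaction (BASIS, AC, and RETI) with time".

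The survey schedule appears in two places.

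- **Section Two, 1.2 Pre-Training Activities.** One week before training the list has "T1 sent for completion", with no arm named. Providers who have not completed T1 are asked to do so in the first minutes of training. After training the list separates the arms: "Following training: send out T2 surveys to be completed by following morning for TF-CBT", and then "Following training: send out T5 surveys, payment, and relevant information for RETI participants".
- **Section Four, 1. Provider Measures.** The list and the table show T1 to T5 with no separation by arm.

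On training length, the Conditions Overview says of RETI: "Providers in this research group received a half-day training and handout in RETI practices". It gives TF-CBT training as 3 days, with BASIS or AC sessions before and after. The TF-CBT description that follows gives 2 days.

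The plan does not say whether time is wave number or elapsed time, or how Model 4 treats RETI in the training piece.

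**The concern.** After a single half-day training, the next survey that the checklist names for RETI is T5. The natural reading is that RETI providers have T1 and T5 only, while BASIS and AC providers have up to five waves over several days.

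A slope through two points depends only on the end points. A slope through five points also depends on when, between T1 and T5, the change occurs. If time is in days, the two slopes are also divided by different lengths of time. A RETI-by-time difference in the training piece could then reflect the survey schedule and not the change in attitudes, norms, self-efficacy or intentions. In addition, if the Section Four table is taken at face value, RETI's absent T2 to T4 would be counted as non-response.

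**Working it through.** The documents give no effect size, power or sample size for Aim 2a, so there is no figure of the plan's own to reproduce. The check gives every arm the same true gain *g* from T1 to T5 and asks what a fitted slope returns.

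**1. Time as wave number (stand-alone straight line over T1 to T5)**

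For waves 1 to 5 the mean is 3 and the sum of squared deviations is 10. The slope is therefore Σ(wave − 3)·y / 10, and the fitted gain is 4 × slope. For RETI, with waves 1 and 5 only, the slope is *g*/4 = 0.25*g* and the fitted gain is *g*. The illustration uses *g* = 0.40 (assumed).

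| BASIS/AC path | Slope | Fitted gain | Error against 0.40 |
|---|---|---|---|
| Linear | 0.25*g* | 0.40 | 0 |
| All gain at T2 | (−1+0+1+2)*g*/10 = 0.20*g* | 0.32 | −20% |
| All gain at T3 | (0+1+2)*g*/10 = 0.30*g* | 0.48 | +20% |
| All gain at T4 | (1+2)*g*/10 = 0.30*g* | 0.48 | +20% |
| All gain at T5 | 2*g*/10 = 0.20*g* | 0.32 | −20% |

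If RETI's two surveys were renumbered 1 and 2, its slope would be 1.0*g* per step, four times the linear BASIS/AC slope.

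**2. The same paths in one possible piecewise fit over T1 to T12**

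This is a continuous line by wave number with knots at T5 and T9, and the gain is held flat after T5. The fitted T1 to T5 gain in BASIS/AC is 0.40 (linear), 0.29 (step at T2), 0.45 (T3), 0.48 (T4) and 0.38 (T5). RETI without T2 to T4 returns 0.40. The size of the error changes with the specification, but its sign still depends on the path.

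**3. Mixed-model check**

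A small random-intercept simulation used assumed values: 50 providers per arm, intraclass correlation 0.6, *g* = 0.5 SD and 40 replicates. The spurious difference from RETI over the segment was about 0 for linear paths, −0.09 to −0.10 SD for a step at T2, and +0.09 to +0.10 SD for a step at T3. This agrees with ±20% of 0.5 SD.

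**4. Time in elapsed days**

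Let L be the days from T1 to the start of training and D the length of the TF-CBT sequence. With equal gains, the RETI slope divided by the TF-CBT slope is (L + D) / (L + 0.5). The 0.5 is RETI's half day. L and D are assumed, because the documents do not fix the dates.

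| L (days) | D = 2 | D = 3 | D = 4 |
|---|---|---|---|
| 0.5 | 2.5 | 3.5 | 4.5 |
| 1 | 2.0 | 2.67 | 3.33 |
| 3 | 1.43 | 1.71 | 2.0 |
| 7 | 1.2 | 1.33 | 1.47 |

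The range is 1.2 to 4.5. For a 3-day sequence the ratio reaches 6 (3/0.5) only at L = 0, with T1 completed as training starts.

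**5. The end-point contrast**

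The T5 minus T1 change returns *g* in every arm, whatever the path between.

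**The case against.** Four objections carry weight.

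- **RETI's missing T2 to T4 is an inference.** A reader might take it as stated, but no section says so. The source is an operations checklist that does not mention T3 or T4 for any arm. The inference is strong, but what the documents establish is that Section Two and Section Four do not match.
- **The target is peripheral.** Aim 2 is about BASIS against AC, the listed interaction terms name only BASIS, and the Model 4 line says no more than that group interacts with time. A RETI training slope follows from the piecewise structure given for Aim 2a and is not written out. Section Six names Aims 1b and 2b as the main analyses.
- **No one-sided bias is shown.** A reader might infer that the plan understates the BASIS and AC gain by 20%, from steps at T2 or T5. Steps at T3 or T4 give the opposite sign, and a linear path gives no error.
- **A six-fold slope difference is not typical.** It needs time in days and T1 at the start of training. The checklist sends T1 a week earlier and uses the opening minutes only for late completers. With L = 7 the ratio is 1.2 to 1.47.

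What remains is that the plan leaves open both the time metric and the RETI schedule, and several ordinary choices would distort the RETI contrast.

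**Conclusion.** The point holds as a minor one about a secondary model. The checklist and the Section Four schedule need to be reconciled. If the checklist is right, a T1 to T5 slope comparison involving RETI cannot be read as a comparison of gains. By wave number the stand-alone error is between −20% and +20%, and it is zero for linear paths. By elapsed days the ratio is about 1.2 to 4.5 under the assumed timings. These figures rest on equal true gains, on RETI having T1 and T5 only, and on assumed paths and dates.

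A reader might infer that the evaluation of BASIS is compromised. It is not. BASIS and AC follow matching session schedules, so Model 3 is unaffected, as are Aims 1b and 2b. Only RETI contrasts in the training piece are at risk.

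**What to change.** 1. State which survey waves each arm received, including whether RETI providers received T6 to T12. If the checklist is confirmed, mark T2 to T4 for RETI in the Section Four table as not collected, so that they do not count as non-response.
2. Define the time metric for Aim 2a. If it is elapsed time, first reconcile the 2-day and 3-day statements of TF-CBT training length.
3. Keep the T1 to T5 slope for BASIS versus AC only (Model 3).
4. In Model 4, compare RETI with the other arms in the training phase on the T5 minus T1 change, with T1 and T5 as categorical occasions.
5. Note beside that result that the contrast does not remove the difference between arms in elapsed time and training content.

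The cost is plan wording and a recoded time variable, with no new data. The downside is that the RETI contrasts will not use the T2 to T4 data from the TF-CBT arms.
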